## 4 STUDY DESIGN AND ENDPOINTS

### 4.1 DESCRIPTION OF THE STUDY DESIGN

This randomized partially blinded study will recruit 120 patients with a history of actinic keratosis (AK) lesions. A control versus study group analysis will be performed where 50% of the subjects will be randomly assigned (balanced by Fitzpatrick skin type, separate randomization lists will be made for type I&II and types III-VI, at time of first visit subjects will be assigned to study or control group by giving them the next assignment on the appropriate list) to use the SHADE sensor and its app (study group), while the other 50% (control group) will receive standard of care UV counseling(placebo). Subjects will have 3 visits. The first and last visit will be standard of care visits at 0 month (enrollment), and the conclusion of their involvement. The second visit will be scheduled 3 months after the enrollment visit. The final visit will be scheduled as soon as practical, but at least 3 months after visit 2 and after September 30. On arrival at each visit, study personnel will pre-screen patients to ensure that the sensor is not visible to physician prior to examination, for example by placing it in their pocket. At each follow up visit, the number of actinic keratosis on the face and hands will be counted and photographed. They will be treated as per standard of care protocol with cryotherapy or curettage. General use of field therapies will not be permitted during the trial. Any lesions suspicious of non-melanoma or melanoma skin cancer will be photographed and biopsied as part of the standard of care algorithm. Cyclobutane pyrimidine dimers (CPD) levels will be measured by ELISA from exposed (cheek) and unexposed (buccal mucosa) skin scrapings collected at the first and last visit. For each patient, the CPD level from exposed skin will be normalized to the sun protected CPD level measured from unexposed skin. We will compare the normalized CPD level of control versus study participants at each timepoint and their average CPD change over time.

We will then compare these levels with Shade UV measurements. Finally, patients will also answer questions in PROMIS (Patient-Reported Outcomes Measurement Information System) in the fields of anxiety, depression and ability to participate socially to gauge their attitudes toward the sensor

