### 7.3.3 FOLLOW-UP

A focused examination of the scalp, face, hands and any other pertinent areas will be performed at the follow up visit(s). AKs will be identified and photographed. Any other suspicious lesions will be biopsied as described as above. AKs will be treated as previously described.

The study coordinator will maintain the schedule of follow up visits and will contact subjects via phone or email. In the event that a subject in the treatment arm is having difficulty achieving compliance, the study coordinator will be available for counseling, training, to provide replacement of broken or lost devices, and encouragement. Calls will be logged in the study binder.

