### ***10.4 DESCRIPTION OF STATISTICAL METHODS***

Actinic keratosis (AK) is a frequent pre-cancerous skin lesion caused by damage from ultraviolet exposure. Without treatment, 1-2% of these lesions evolve into squamous cell carcinoma (SCC). Therefore, the number of AKs reflects the effect of UV exposure and the risk for SCC. Transplant patients are at high risk of skin cancer because of their immunosuppressive medications required to prevent organ rejection. Morbidity/mortality of SCC in this patient population can be as high as 25%.

The primary outcome of this trial will be a statistically significant reduction by at least 25% in the cumulative number of newly developed AK lesions between the control and the study group.

AK lesions on sun exposed skin areas (scalp, face, hands) will be counted and reported by dermatologists at enrollment and at each subsequent visit. AKs are defined as keratotic macule(s) or papule(s) on an erythematous base by dermatological examination. In addition to the enrollment visit, this study will include a follow up dermatological visit after the summer. For each patient, the number of newly occurred AKs will correspond to the cumulative AK counts during the study period. To insure that only new occurrences of AK lesions after V1 will be counted, data from subsequent study visits will include the location of AK lesions and pictures of the lesions.

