#### 10.4.1 GENERAL APPROACH

All tests will be two-tailed with the significance level set at 0.05. Analysis will be performed using STATA statistical software (StataCorp. 2015) or R (R: A language and environment for statistical computing. R Foundation for Statistical Computing, Vienna, Austria).

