#### 10.4.2 ANALYSIS OF THE PRIMARY EFFICACY ENDPOINT(S)

##### **#1 (Primary): Quantify the impact of Shade on the cumulative number of new actinic keratoses developed over the study period.**

To test our primary aim, we will perform a control versus study group analysis. The study group will receive a Shade sensor and Shade app while the control group will standard of care sun avoidance counseling. The study will be randomized and single-blinded as described in section 10.6.1. This will also allow us to control for the effect of UV level variation on the primary outcome since the two groups will have balanced enrollment dates. All the patients will receive recommendations about UV exposure protection as defined by the recommendations of the American Academy of Dermatology and the National Cancer Institute.

Patients who will have used the Shade sensor for less than 15% of the days over the study period will be excluded from these analyses. We will use a Student's t-test with the following null and alternative hypothesis:

$$H_0: \text{mean}^C_{t12} (\text{AK}) = \text{mean}^I_{t12} (\text{AK})$$

$$H_a: \text{mean}^C_{t12} (\text{AK}) \neq \text{mean}^I_{t12} (\text{AK})$$

where  $\text{mean}^C_{t12} (\text{AK})$  is the averaged cumulative number of AK between enrollment follow up of controls and  $\text{mean}^I_{t12} (\text{AK})$  is the averaged cumulative number of AK of intervention patients.

In this analysis, demographic and clinical factors such as gender, age, baseline count of AKs, skin type, immunosuppressive treatment and comorbidity can be confounding factors. To test and control for confounding, demographic and clinical data (skin type, living area, gender, age, count of AK at enrollment, immunosuppressive (IS) treatment, level of immunosuppression and comorbidity) will be collected. We will use a stepwise multivariate approach with backward selection: 1) the effect of potential confounding factors will be tested using the same statistical tests, 2) factors with p-value <0.2 and less than 25% of missing values will be included in the multivariate model and 3) only covariates with significant adjusted p-value (<0.05) will be kept in the final model. Clinically relevant interactions will also be tested (e.g. skin type, gender, age) and kept in the final model if significant. The adjusted effect of Shade use will be estimated using a multivariate linear regression.

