### 10.5 SAMPLE SIZE

The most efficient approach to performing the power calculation for this study via Monte Carlo simulation as the underlying phenomenon, AK rate, is best modeled by a Poisson distribution.

As a starting point, we took the distribution of AK rates from actual clinical data. The data were assembled by querying EPIC on 2014 visits of kidney transplant patients to dermatology (this subset of the population will have fewer AK's than the non-transplant subjects and therefore use of this distribution will err on the side of caution toward overpowered the study). For each visit in which the dermatologist chose to treat by LN2 destruction, the query retrieved the number of procedures performed. This approach is conservative as the input data potentially underestimates AK count as some AK's may not have been treated.

The structure of the Monte Carlo was straightforward. A set of potential study sizes (N recruited) and effect sizes were chosen. For each input condition, two thousand random experiments were performed. In each of these interactions, baseline AK rates were drawn from the clinically observed distribution of AK's. Subjects were sequentially assigned to treatment or control groups. Observed AK rates were generated using a Poisson distribution for each visit. The analysis expected for the study was then performed. In this analysis the total count of AK's for each subject was obtained and the means and distributions compared for directionality (AK\_treated < AK\_control) and significance (p-value from a one-tailed t-test).

Analysis was performed in R (R Open 3.2.3) with statistical calculations and random number generation using the base and stat libraries.

[figure not shown]

Figure 10.5.1. With an effect size of 0.25 and recruitment of 100 patients (50 treatment, 50 control) we predict a power of 0.81.

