#### **14.3 PROTOCOL DEVIATIONS**

Protocol deviations will be reported to the sponsor and the IRB within 72 hours. The following events are expected and should be marked on the CRF but do not require reporting as deviations:

1. Rescheduled visit. While visits should be scheduled within 7 days of the target visit date, visits may be rescheduled within 21 days of the visit target date.
2. Screen fail. A subject may be enrolled based on passing screening questions but subsequently dropped if there is evidence in their medical record that they have failed screening. In that event the subject's CRF will indicate a screen fail (by initialing the appropriate CRF) and the subject will be dropped from the study.

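### The primary analysis of cumulative AK counts has no term for time at risk, while the final visit has no latest date and is booked by a coordinator who knows the arm

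*Combined protocol and SAP*

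**What the plan says.** - **Outcome and test.** Section 10.4 defines the outcome as a count: "the number of newly occurred AKs will correspond to the cumulative AK counts during the study period". Section 10.4.2 compares the arm means: "We will use a Student's t-test with the following null and alternative hypothesis". A linear regression with backward selection follows. Its candidate covariates do not include follow-up time or visit date.
- **Timing of the final visit.** Section 4.1: "The final visit will be scheduled as soon as practical, but at least 3 months after visit 2 and after September 30". Section 14.3 says that "visits may be rescheduled within 21 days of the visit target date", but no target date is set for the final visit.
- **Who books it.** Section 7.3.3: "The study coordinator will maintain the schedule of follow up visits and will contact subjects via phone or email". Under sections 7.3.2 and 10.6.1 the same coordinator holds the randomization table and schedules the next visit or visits after the assignment is drawn.
- **Stated protection.** Section 10.4.2 relies on the two groups having balanced enrollment dates.
- **Analysis table.** Section 10.4.10 lists a cumulative AK count at follow-up and no date or duration column.
- **Elsewhere in the plan.** Section 10.5 says that "the underlying phenomenon, AK rate, is best modeled by a Poisson distribution", and the squamous cell carcinoma analysis (#3) includes time since enrollment. The primary analysis uses neither a count model nor time.

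**The concern.** A cumulative count depends on how long the patient was observed. Balanced enrollment dates equalise the start of follow-up. The end is fixed after randomization, through an open-ended booking made by someone who knows the arm. If one arm came back sooner on average, its count would be lower for that reason alone, and the comparison of means would attribute the gap to the device. If the study arm came back later, a real benefit would be diluted. With no follow-up time in the test, the covariate list or the analysis table, neither case would show in the planned output. The endpoint at stake is the primary one.

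**Working it through.** **1. The plan's own figure.** Section 10.5 gives power 0.81 for a 25% reduction with 50 per arm and a one-tailed t-test. The clinical AK distribution behind it is not tabulated, so it cannot be reproduced directly. It can be solved backwards for the coefficient of variation (CV) of a patient's count:

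power = Φ(0.25 / (CV × √(2/n)) − z)

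- One-sided, n = 50: CV 0.496 gives 0.25/0.0992 = 2.52, and 2.52 − 1.645 = 0.875, so power 0.81.
- Two-sided, n = 50: CV 0.441 gives 0.25/0.0882 = 2.83, and 2.83 − 1.96 = 0.87, so power 0.81.

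The plan therefore implies a CV of about 0.44-0.50.

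**2. How far follow-up can vary.** Under section 4.1 the minimum follow-up is about 8.5 months for a mid-January enrollee, 7.5 for mid-February, 6.6 for mid-March and 6 from April on, with no maximum. Randomization balances the part due to enrollment date in expectation. Only the part set after randomization is at issue.

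**3. Inputs for the illustration.** From the documents: 60 per arm (120 recruited, section 4.1) and a two-sided 0.05 level (section 10.4.1). Assumed: follow-up uniform over 26-38 weeks (mean 32), CV of the patient's AK rate 0.3-0.5, mean count 6-12, no device effect, study arm seen 2 or 4 weeks earlier.

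Total CV² = rate CV² + 1/mean + follow-up CV², where follow-up CV = (12/√12)/32 = 0.108.

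- Rate CV 0.3, mean 12: 0.090 + 0.083 + 0.012 = 0.185, CV 0.43.
- Rate CV 0.5, mean 6: 0.250 + 0.167 + 0.012 = 0.429, CV 0.65.

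This range contains the 0.44-0.50 of step 1.

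**4. Constant AK rate.** Apparent reduction = gap/32, that is 2/32 = 6.25% and 4/32 = 12.5%. The standard error of the relative difference is CV × √(2/60), or 0.0785 to 0.1195.

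- 2 weeks: 0.0625/0.0785 = 0.80 and 0.0625/0.1195 = 0.52. P(Z > 1.96 − 0.80) = 12% and P(Z > 1.96 − 0.52) = 7.5%.
- 4 weeks: 0.125/0.0785 = 1.59 and 0.125/0.1195 = 1.05. The same step gives 36% and 18%.

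Simulation agrees: about 8-13% and 19-37%. A separate simulation with counts calibrated to the 0.81 power and a 6-month base gave 10-11% at 2 weeks and 28-30% at 4 weeks.

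**5. Slower accrual after summer.** The open-ended time falls after September 30. Assume that accrual drops to a fraction r after week 20, so effective weeks = 20 + r × (T − 20). At T = 32 this is 26 for r = ½ and 23 for r = ¼.

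| Study arm earlier by | Reduction, constant rate | Reduction, r = ½ | Reduction, r = ¼ | False benefit, constant rate | False benefit, r = ½ or ¼ |
|---|---|---|---|---|---|
| 2 weeks | 6.25% | 1/26 = 3.8% | 0.5/23 = 2.2% | 8-13% | 4-8% |
| 4 weeks | 12.5% | 2/26 = 7.7% | 1/23 = 4.3% | 19-37% | 6-18% |

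The false-benefit columns are simulated; the nominal value is 2.5%.

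**6. With the 25% criterion.** Section 10.4 asks for significance and a reduction of at least 25%. If that means an observed reduction, the constant-rate figures fall to 0.2-3.4% at 2 weeks and 3-11% at 4 weeks.

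**7. Which time adjustment works.** A fixed log(days) offset is exact at a constant rate. If accrual slows, it over-corrects. For a 4-week gap the expected null rate ratio is (24/28)/(26/32) = 1.05 at r = ½ and (22/28)/(23/32) = 1.09 at r = ¼, against an arm that returns early. Simulated false harm over the slowed settings is 4-19%. With log(days) as a covariate whose slope is estimated, each tail stayed at about 2-4% in every setting run.

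**The case against.** The main objection is that no passage shows or predicts a difference in follow-up between arms. A reader might infer that the plan will produce a spurious device benefit, or that the coordinator will book the arms differently. The documents support neither. The direction is open: the monthly usage payment in section 5.3, for the study arm only and for up to 12 months, could lengthen follow-up there and count against the device.

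The asymmetry in contact is also limited. The schedule of events (7.3.7) lists compliance engagement with no arm restriction, and extra counselling in the treatment arm is conditional on difficulty with compliance (7.3.3). Both arms are paid $50 per visit.

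Some wording restrains drift: the final visit is to be as soon as practical, patients who cannot keep quarterly visits are dropped (5.4.1), and duration is given as 9-12 months (6.1.9). None of these sets a closing date, and 9-12 months does not match the 6-month minimum that section 4.1 allows.

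A reader might also assume that counts move in proportion to days observed. That needs a constant AK rate, which a study built around one summer does not guarantee.

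These points stand, and they limit the size and certainty of the harm. They do not supply the missing time term or the missing latest date.

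**Conclusion.** The gap is real and conditional: if follow-up came to differ by arm, in either direction, the planned t-test and regression would neither detect nor adjust for it. The sizes in the working rest on an assumed gap, AK distribution and accrual pattern, because the documents give none of these. They show that a gap of a few weeks could matter, not that one will occur.

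A count model should not be sold on power. With equal follow-up and counts calibrated to the plan's stated power, it gave 0.80-0.81 against 0.80 for the t-test. The gain is protection of the primary comparison, and a rate ratio that estimates the 25% reduction directly. This is a cheap improvement to the plan and does not invalidate the design.

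**What to change.** 1. **Section 4.1:** set a target date for the final visit, so that the 21-day window in section 14.3 applies to it. This comes first, because a model cannot fully repair follow-up that differs by arm.
2. **Section 10.4.10:** add the V1, V2 and V3 dates, or days of follow-up, and report follow-up time by arm.
3. **Section 10.4.2:** analyse new AKs after V1 with a quasi-Poisson or negative binomial log-link model. Include treatment and log(days from V1 to last count) as a covariate with estimated slope, kept in the model whatever the backward selection does. Report the rate ratio with its 95% CI, with a fixed log(days) offset as a sensitivity analysis.
4. **Endpoint #2:** use log(days from V2 to V3) in the same way.

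The cost is a model in place of a t-test, a small addition to the analysis table and one more summary table. Section 8.6 already has staff record all visits, so the dates should be available. No extra patients or procedures are needed, and no power is lost when follow-up is alike in the two arms. If it does differ, separating time from treatment costs some precision.

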### 5.4.2 HANDLING OF PARTICIPANT WITHDRAWALS OR TERMINATION

Subject compensation will not be affected by study withdrawal or termination. Each endpoint will be analyzed using only data for which there is a complete data set relevant to that analysis.

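### The adjusted primary model loses randomised patients with a known AK count when a fitted baseline covariate is blank, which costs precision and comparability

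*Combined protocol and SAP*

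**What the plan says.** Section 10.4.2 gives the primary endpoint two analyses.

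- **Unadjusted.** "We will use a Student's t-test with the following null and alternative hypothesis". This compares mean cumulative AK counts and uses no covariates.
- **Adjusted.** The candidates are "skin type, living area, gender, age, count of AK at enrollment, immunosuppressive (IS) treatment, level of immunosuppression and comorbidity". On entry, "factors with p-value <0.2 and less than 25% of missing values will be included in the multivariate model". On retention, "only covariates with significant adjusted p-value (<0.05) will be kept in the final model". Then "The adjusted effect of Shade use will be estimated using a multivariate linear regression".

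Section 5.4.2 adds: "Each endpoint will be analyzed using only data for which there is a complete data set relevant to that analysis". Nothing in the protocol describes imputation, a missing category or a sensitivity analysis for blank covariates.

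Section 10.4.3 reuses the primary procedure for endpoint #2 and a similar stepwise approach for endpoints #3 and #4.

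Section 17.1 records that a kidney transplant is no longer required for entry. Level of immunosuppression nevertheless remains a candidate covariate, and no code is given for patients who are not on such therapy.

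**The concern.** A linear regression fitted to complete data omits any patient with a blank in a fitted covariate. The under-25% limit applies to each factor separately, so it does not cap the total loss when several factors are fitted. In a randomised trial a blank baseline item is no reason to discard a patient whose outcome was observed.

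Two things are at stake. The first is precision: adjustment is meant to narrow the interval for the Shade effect, and lost patients widen it. The second is comparability: if the unadjusted and adjusted estimates come from different patients, a reader cannot tell whether a difference between them reflects adjustment or the change of patients.

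**Working it through.** **The plan's own figure.** Section 10.5 gives a power of 0.81 for 100 patients (50 per arm) and a 25% effect, by simulation of a one-tailed t-test. It cannot be reproduced, because the clinic AK distribution is not shown. Working back with the normal approximation and an assumed one-sided 0.05 level gives a standardised difference of (1.645 + 0.878) × √(2/50) ≈ 0.505. That figure belongs to a test without covariates, so it is not used below.

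**Inputs.** N = 120 (Section 4.1), before withdrawals and before the exclusion for sensor use below 15% of days. Missing share m is below 25% per factor (Section 10.4.2). The documents give no actual rates, so every value of m is an assumption inside that limit.

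**Patients left and interval width.** With k fitted factors, each missing a share m independently, the number left is 120 × (1 − m)^k. At unchanged residual variance the interval widens by √(120 / number left).

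| Fitted factors (assumed gaps) | Left of 120 | Width ratio |
|---|---|---|
| One, 2% | 118 | 1.01 |
| One, 10% | 108 | 1.05 |
| One, 24% | 91 | 1.15 |
| Two, 10% each, independent | 97 | 1.11 |
| Two, 24% each, independent | 69 | 1.32 |
| Two, 24% each, same patients | 91 | 1.15 |

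**Changing patient sets.** Suppose two factors are admitted, each 10% blank independently, and one is retained. The t-test uses 120 patients and the model with both admitted factors uses 97. The final model uses 108 if refitted on everyone complete for the retained factor, or 97 if the selection sample is kept. The plan does not say which.

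**Gain against loss.** Relative to the unadjusted comparison, the variance of the adjusted effect is roughly (1 − R²)/(1 − m), where R² is the share of outcome variance that the covariate explains. The covariate repays its losses only if R² exceeds m. Retention at p < 0.05 asks for much less. The smallest retained partial R² is about t²/(t² + df). With about 91 patients this is 1.99²/(1.99² + 88) ≈ 0.04, and with 108 it is also about 0.04. The plan could therefore keep a covariate that explains 4% of the variance while giving up 10% or 24% of the patients.

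**Where blanks are plausible.** Skin type is needed for randomisation (Section 10.6.1). The AK count is taken by examination at enrolment (Section 10.4). Age is an eligibility item (Section 5.1), and gender is a reported demographic (Section 10.4.6). That leaves mainly living area, comorbidity and level of immunosuppression.

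**The case against.** **The primary test loses nobody.** This stands in full. A reader might infer that blank covariates cut the power of the primary comparison. They do not: the stated hypotheses are tested by a t-test that needs no covariates, and the power simulation was for that test. Power figures obtained by shrinking N would describe no planned analysis and would ignore variance explained by baseline AK count.

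**The blanks may be few.** Much of this stands. History is taken at enrolment, the medical record is a source for the case report form (Section 11), monitors verify source data (Section 9), and tables are frozen only after queries are resolved (Section 10.6.3). Overlapping gaps cost no more than the worst single factor. The row with 69 patients needs two factors each almost a quarter blank, in unrelated patients, and both fitted.

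**Only retained factors matter at the end.** This is true of the final model if it is refitted. It does not help the selection step, and it is why the patient sets can differ.

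**The immunosuppression covariate.** One might infer that it removes most of the trial, since "immunosuppressive (IS) treatment, level of immunosuppression and comorbidity) will be collected" although transplant is no longer required. The documents do not support that. A factor blank for most patients is barred by the under-25% limit, the transplant share is not stated, and nothing says that untreated patients would be left blank. What stands is that the coding is unspecified.

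**The complete-data sentence concerns withdrawals.** It sits under that heading and does not mention covariates. It is nevertheless worded for each endpoint, and no other rule exists.

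**This is only a by-product of stepwise selection.** In part. Fixing a short list of nearly complete covariates in advance would remove most of the exposure, but the plan does not do so.

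**Conclusion.** The point holds for the adjusted primary model and for the adjusted analyses of endpoints #2 to #4. As written, a randomised patient with a known outcome leaves the model for a blank baseline item, and the analysed patients can change between steps.

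For one retained covariate with 10% or 24% missing, the cost is 12 or 29 of 120 patients and an interval about 5% or 15% wider. This assumes those missing shares and unchanged residual variance. The true cost may be close to nothing, and it exceeds the single-covariate figure only when several retained factors have gaps in different patients.

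A reader might also infer bias between arms. The documents do not show it: history and examination come before the assignment is disclosed to the patient, and the examining physician is blinded, so blanks should not depend on arm. The issue is precision and comparability of a supporting estimate. It is worth settling before the blind is broken, because the remedy is cheap.

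**What to change.** Keep the under-25% limit as an entry cap, since it is the only limit on missingness, and add to Section 10.4.2:

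> No randomised patient with an AK outcome is dropped from the adjusted model for a missing baseline covariate. Missing continuous covariates are set to the mean of the pooled arms, and missing categorical covariates form their own category, without reference to arm. The t-test, selection steps and final model use the same patients.

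Code level of immunosuppression as none for patients not on such therapy, so that it is not treated as missing. Apply the same rule to endpoints #2 to #4, and state in Section 5.4.2 that the complete-data rule does not extend to baseline covariates.

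The cost is one SAP paragraph and no extra data. The downside is slightly weaker adjustment where values are filled in. With gaps unrelated to the values, a mean-filled covariate explains about (1 − m) × R². At m = 0.24 and R² = 0.24 the relative variance is 1 − 0.76 × 0.24 ≈ 0.82, against 0.76/0.76 = 1.00 when those patients are dropped. The change does not address the p-value selection itself, which is a separate matter.

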#### 10.4.3 ANALYSIS OF THE SECONDARY ENDPOINT(S)

##### **#2 (Secondary): Quantify the impact of Shade on the numbers of new AK's observed at the final visit**

This analysis will follow the same procedure as the primary analysis but will only include AK data from the final visit.

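### Keeping significant interactions can turn the adjusted Shade effect into a reference-level effect picked by the data, and the plan gives no rule for recovering the average effect

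*Combined protocol and SAP*

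**What the plan says.** Section 10.4.2 has two layers. The primary hypothesis compares two group means: "We will use a Student's t-test with the following null and alternative hypothesis". That test has no covariates and no interaction step.

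A stepwise model to control confounding follows. Factors are screened at p<0.2, and then "only covariates with significant adjusted p-value (<0.05) will be kept in the final model". Next comes the interaction rule, "Clinically relevant interactions will also be tested (e.g. skin type, gender, age) and kept in the final model if significant", and then the estimate: "The adjusted effect of Shade use will be estimated using a multivariate linear regression".

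Section 10.4.1 sets the level: "All tests will be two-tailed with the significance level set at 0.05". In section 10.4.3, endpoint #2 takes over the whole procedure: "This analysis will follow the same procedure as the primary analysis but will only include AK data from the final visit". Endpoints #3 and #4 use a similar stepwise approach, without saying whether the interaction step comes with it. Section 10.4.8 marks sub-group analyses as not applicable, and section 10.4.9 says there are no multiple comparisons.

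The plan does not state whether the interactions are with study group, how many will be tested, how factors are coded or centred, or how one Shade effect is obtained once an interaction is in the model.

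**The concern.** A model containing a Shade-by-factor term has no single Shade effect. The coefficient labelled Shade is the effect where the factor equals zero: one gender, one skin-type group, or age zero. The hypotheses in 10.4.2 concern the difference in means over the whole trial population.

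Under the rule, the adjusted result is the population-average difference in some data sets and a subgroup effect in others, and a test on the same outcome data decides which. The selected coefficient is also more likely to be extreme, because its estimate is correlated with the interaction estimate that triggered the selection. The adjusted effect of Shade on new AKs, for the primary endpoint and for endpoint #2, could then be reported with a p-value and interval that do not have their nominal properties.

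**Working it through.** **The plan's own figures.** The only error rate stated for this step is the nominal 0.05. The plan's power figure ("With an effect size of 0.25 and recruitment of 100 patients (50 treatment, 50 control) we predict a power of 0.81") concerns the t-test. With a 25% reduction and 50 per arm, 0.81 requires SD / control mean = 0.495 at one-sided 0.05 (alpha assumed) or 0.440 at two-sided 0.05. The AK distribution is not given, so 0.81 can be neither confirmed nor refuted, and the point below does not depend on it.

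**Why the coefficient changes meaning.** Write Y = b0 + b1·T + b2·X + b3·T·X, with T = 1 for Shade. The effect at X is b1 + b3·X, and the average effect is b1 + b3·mean(X). They agree with b1 only if mean(X) = 0, that is, if X is centred.

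**Why selection inflates error.** The correlation between the estimates of b1 and b3 is −m/√(m² + s²), where m and s are the mean and SD of X.
- 50/50 binary factor, 0/1 coding: m = 0.5, s = 0.5, correlation = −0.5/√0.5 = −0.71.
- Uncentred age, assumed mean 65 and SD 9: −65/√(4225 + 81) = −65/65.6 = −0.99.
- Centred factor: m = 0, correlation 0.

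Selecting on a large b3 therefore selects a large b1 of opposite sign, unless X is centred.

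**How often a term is kept by chance.** With three null interactions at 0.05: 1 − 0.95³ = 0.143. With eight: 1 − 0.95⁸ = 0.337. Simulation gave 0.134–0.150 and 0.322–0.339.

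**False-positive rate of the final Shade coefficient.** These are simulations with no Shade effect and no interaction, 100 or 120 patients in equal arms, and 5,000 to 20,000 trials per setting. Assumed, because the documents do not supply them: binary skin type and gender; age mean 65, SD 9, limited to 18–80; outcomes normal or gamma-Poisson counts.

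| Reading of the rule | Rate |
|---|---|
| No interaction step, adjusted model | 0.046–0.057 |
| Unadjusted t-test | 0.045–0.055 |
| Interactions kept, all factors centred | 0.050–0.053 |
| One interaction, reference coding | 0.063–0.064 |
| Three, two binary plus centred age | 0.068–0.072 |
| Three, all binary | 0.080–0.093 |
| Three, two binary plus uncentred age | 0.105–0.112 |
| Eight interactions | 0.137–0.167 |

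The pieces add up. With three binary factors and counts, a term was kept in 0.134 of trials and 0.270 of those were falsely significant: 0.134 × 0.270 = 0.036 of the total 0.081. With uncentred age: 0.141 × 0.464 = 0.065 of the total 0.105.

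**The full sequence in 10.4.2** (screen at 0.2, backward elimination at 0.05, then interactions; normal outcome; 8,000 trials, so the simulation error near 0.05 is √(0.05 × 0.95/8000) ≈ 0.002):
- all three interactions tested: 0.085–0.098 with binary age, 0.118–0.120 with uncentred age;
- tested only for retained covariates, factors not prognostic: 0.055–0.060, against 0.053–0.057 without the interaction step, so a negligible rise;
- tested only for retained covariates, factors prognostic: 0.083–0.101;
- all factors centred: 0.052.

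**A different assumed population** (60 per arm, gamma-Poisson counts with control mean about 5 and shape 3, sex 60/40, skin type 70/30, age mean 62, SD 10) gave the same picture over repeated runs: 10.0–11.2% with uncentred age, 6.4–8.0% with age centred, and 4.9–5.5% with all factors centred.

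**When Shade works.** A uniform 25% reduction is multiplicative. If one group has 1.5 times the AK rate m of another, the absolute reductions are 0.25m and 0.375m, so raw counts show an interaction although the relative effect is the same. With assumed rate ratios of 1.5 (sex), 0.6 (skin type) and exp(0.3) per 10 years of age, a term was kept in about 19% of trials.

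**The case against.** The strongest reply is that the confirmatory test is not involved. A reader might infer that the trial's primary false-positive rate doubles. The documents do not support that: 10.4.2 writes the null and alternative for two group means and tests them with an unadjusted t-test, which stayed at about 5% throughout. This stands. What remains open is that the plan does not say which result governs if the t-test and the adjusted estimate disagree.

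Second, the interaction sentence closes a paragraph on confounder selection and never says the terms involve study group. Covariate-by-covariate terms, such as age by skin type, would not alter the meaning of the Shade coefficient, and the not-applicable entry for sub-group analyses fits that reading. This stands as a limit: the Shade-by-factor reading is an inference. It is the natural one, because single factors are named and the model exists to estimate the Shade effect.

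Third, the inflation arises only if an analyst reads a raw reference-level coefficient as the adjusted effect. Centring, or averaging over the factors, restores about 5%. That is correct, but nothing in the plan requires either.

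A reader might also infer that the rule commonly makes an effective device look harmful. With uncentred age, 60–68% of the trials that kept a term had a Shade coefficient pointing toward harm. That is mostly an effect extrapolated to age zero. The share falls to 10–17% with age centred and 1–3% with all factors centred, against 2% for the model without interactions. Even uncentred, 0.68 × 0.19 is about 13% of all trials. The rate ratios behind these figures are assumptions, so they should not be used as the size of the problem.

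**Conclusion.** The concern holds for the adjusted estimate. On the Shade-by-factor reading, the stated rule lets a test on the same data replace the average difference between groups with a reference-level effect, and no other section repairs this.

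The size depends on choices the plan leaves open. The false-positive rate of the adjusted Shade coefficient is about 5% with all factors centred, about 6–12% for the three named factors under reference coding (highest with uncentred age), and up to about 17% with eight interactions. These come from simulations with assumed outcome and covariate distributions, so the range is the result, not any single value within it. The primary t-test keeps its level. Endpoint #2 inherits the rule expressly.

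This should be fixed, but it does not undermine the primary hypothesis test.

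**What to change.** In section 10.4.2, delete the clause that keeps significant interactions in the final model. State that the adjusted Shade effect comes from a model with no data-selected Shade-by-covariate terms. An alternative that serves equally well for error control is to prespecify that the average Shade effect, with all factors centred, is reported whether or not interactions are present.

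Report the Shade interactions with skin type, gender and age separately, labelled exploratory, each with its estimate and interval and whatever its p-value. A short statement that the adjusted estimate supports the t-test, and does not replace it, would settle which result governs.

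Endpoint #2 follows automatically through its cross-reference. For endpoints #3 and #4, say whether any interaction step applies. The cost is one or two sentences, with no new data and no change to the sample size. The change should be made before the blind is broken.
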